8.6 Secondary outcome measures

The secondary outcome measures are divided in three areas:

- Safety
- Performance
- Utility

8.6.1 Safety

- Number of patients experiencing a device-related SAE (SADE) from V09 (month 12) to V13 (month 36). This parameter will be analysed using a frequency table.
- Incidence, nature, severity and seriousness of observed adverse events and adverse device events at any time from V09 (month 12) throughout V13 (month 36). This parameter will be analysed using a frequency table.

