4.2.2 Secondary endpoints

Safety:

Number of patients experiencing a device-related SAE (SADE) at any time from V09 (month 12) throughout V13 (month 36).

Incidence, nature, severity and seriousness of observed adverse events and adverse device events at any time from V09 (month 12) throughout V13 (month 36).

Performance:

Incidence, nature and seriousness of observed device malfunctions during from V09 (month 12) throughout V13 (month 36).

Repeatability of ARGOS-SC measurement

Utility

User acceptance of the ARGOS-SC system at the investigational site by means of evaluation of physician acceptance questionnaires (by investigators)

User acceptance of the ARGOS-SC system at home by means of evaluation of patient acceptance questionnaires (patients)

5 Sample Size and Power

Given by the exploratory nature of this study, the sample size is not driven by the need for a formal statistical hypothesis test with a certain degree of power. Instead, this study is driven by the desire to obtain a clinically meaningful amount of data to evaluate the long-term safety and performance of the ARGOS-SC system in patients who have been already implanted with the study device. Therefore, the maximum sample size is 24. The minimal sample size for this study is at the Sponsor's direction. This is considered to be appropriate since no experimental treatments are planned and all assessments with exception of IOP measurement using the ARGOS-SC device are established standard methods.

6 Analysis Sets

There will be only one analysis set defined in this study:

- **Full Analysis Set (FAS):**

The FAS defined according to the intention-to-treat principle will include all patients of the ARGOS-SC01 clinical investigation with an implanted ARGOS-SC pressure sensor and given their informed consent.

7 Statistical Considerations

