7.1 Derived variables

The table below provides the list of derived variables applicable for this study.

Variables	Formula
Demographic and baseline characteristics	
Age [years]	Year of baseline visit – year of birth
Derivation of duration	
Study duration [days]	Date of patient's last visit or date of study discontinuation (whatever the later date is) – date of baseline visit + 1

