8.1.2 Statistical outputs

8.1.2.1 Tables and graphics

Percentages will be based on the number of subjects in the analysis set.

Categorical variables will be summarized by the number of patients (n) and percentages (%). Percentages will be rounded to one decimal place.

In addition, for the primary endpoints (response rates) the 95% confidence intervals will be calculated.

Continuous variables will be summarized using descriptive statistics, including

- number of patients with non-missing data (n)
- arithmetic mean (Mean)
- 95% confidence interval of mean (if indicated)
- standard deviation (SD)
- median (Median)
- lower (25%, Q1) and upper (75%, Q3) quartile
- minimum (Min) and maximum (Max).

Analyses by visit will be performed irrespective of any time window deviations.

Some mock-up tables are presented in the appendix of this SAP.

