8.8 Further safety analyses

8.8.1 Adverse events

All safety analyses will be conducted on the FAS set.

The AE terms will be coded according MedDRA into System Organ Class (SOC) and Preferred Terms (PT) of *Implandata Ophthalmic Products*.

Number of adverse events as well as the number and relative frequency of patients reporting adverse events will be tabulated by System Organ Class and Preferred terms.

The incidences of AEs will be stratified by:

- Seriousness
- Severity
- Relationship to medical device
- Expectedness
- Action taken
- Outcome
- Criterion to classify as serious

The incidence of AEs will be summarized to include only one occurrence of an AE class per patient. If a patient has multiple AEs of the same class, then that term will only be counted once. All AEs will be listed.

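### SADE and AE incidence over months 12–36 will be shown as bare percentages of the FAS, with no interval and no allowance for follow-up time, in at most 24 patients

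*SAP*

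**What the plan says.** SAP 8.6.1 names two safety endpoints over V09–V13. The first is "Number of patients experiencing a device-related SAE (SADE) from V09 (month 12) to V13 (month 36"); the second is the incidence, nature, severity and seriousness of adverse events and adverse device events. For each it says "This parameter will be analysed using a frequency table".

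The denominator follows from three statements. SAP section 6 says "There will be only one analysis set defined in this study", namely the FAS. SAP 8.8.1 says "All safety analyses will be conducted on the FAS set". SAP 8.1.2.1 says "Percentages will be based on the number of subjects in the analysis set".

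For proportions, intervals are promised in one place only, SAP 8.1.2.1: "for the primary endpoints (response rates) the 95% confidence intervals will be calculated". SAP 8.1.3 fixes the level of any interval that is calculated (two-sided 95%) but adds none for safety. The mock-up of Table 3.1.1 has columns for number of AEs, number of patients and percentage.

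Follow-up time is available. SAP 7.1 derives "Study duration [days"], and Listing 2 prints it per patient. It enters no rate. SAP 7.3 analyses patients as far as they are documented. Protocol 9.8 evaluates early leavers in the same way as completers, and protocol 8.3.2.2 does not replace them.

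Protocol 7.3 and 8.1.2 say that incidence will be set against literature on standalone non-penetrating glaucoma surgery. No reference rate or margin is given.

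**The concern.** Long-term safety is half of the stated purpose of the study. There is no control group, so the reported incidence itself has to carry the comparison with the literature. A percentage from at most 24 patients, without an interval, does not show how wide a range of true risks it is compatible with. The minimum sample size is left to the sponsor (SAP section 5), so the number could be smaller still.

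The second issue is time. A patient who leaves event-free at month 18 has been observed for 6 of the 24 months but weighs in the denominator like a completer. Read as incidence over months 12–36, the printed percentage is then too low. Published rates may rest on a different length of follow-up, and without patient-time the reader cannot align the two.

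**Working it through.** The documents contain no safety rate, margin, precision target or drop-out rate, so there is no stated safety figure to reproduce. The 24 is a cap given without a calculation (SAP 3.3 and section 5).

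**Inputs from the documents:** at most 24 patients; at most 24 months each (protocol 8.3.5), hence at most 24 × 2 = 48 patient-years; two-sided 95% level (SAP 8.1.3).

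**Step 1: what a low count leaves open.** Exact (Clopper-Pearson) limits. For zero events the upper limit is 1 − 0.025^(1/n); for n = 24 this is 14.2%.

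| Patients with event | Shown as | Exact two-sided 95% interval |
|---|---|---|
| 0/24 | 0.0% | 0–14.2% |
| 1/24 | 4.2% | 0.1–21.1% |
| 2/24 | 8.3% | 1.0–27.0% |
| 0/20 (n assumed) | 0.0% | 0–16.8% |
| 0/18 (n assumed) | 0.0% | 0–18.5% |

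The chance of seeing no event in 24 patients is 0.95^24 = 29% if the true risk is 5%, and 0.90^24 = 8% if it is 10%.

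**Step 2: the effect of early leavers on the FAS percentage.** Assumptions, none of them from the documents: true 24-month risk 10%, constant hazard, and a fraction d of patients leaving at times spread evenly over the 24 months.

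- Hazard: h = −ln(0.90)/2 = 0.0527 per year.
- Expected proportion of leavers with an event before leaving: 1 − (1 − e^(−2h))/(2h) = 1 − 0.10/0.1054 = 5.1%.
- Expected percentage shown: (1 − d) × 10% + d × 5.1%.
- Patient-years: 24 × [(1 − d) × 2 + d × 1].
- Upper limit for zero events per 100 patient-years (exact Poisson): 100 × 3.689 / patient-years, where 3.689 = −ln(0.025).

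| Drop-out d | Shown (true 10%) | Shown if all leave at once | Patient-years | Upper limit, 0 events, per 100 patient-years |
|---|---|---|---|---|
| 0% | 10.0% | 10.0% | 48.0 | 7.7 |
| 10% | 9.5% | 9.0% | 45.6 | 8.1 |
| 20% | 9.0% | 8.0% | 43.2 | 8.5 |
| 40% | 8.0% | 6.0% | 38.4 | 9.6 |

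**Step 3: compare the two.** With even drop-out of 10–20%, the percentage falls by 0.5 to 1.0 points. The interval around a single event in 24 is 21 points wide. The absence of an interval therefore matters more than moderate drop-out.

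**The case against.** The best defence is that the study calls itself exploratory, plans descriptive analysis only, and shows its data. Disposition and reasons for drop-out are tabulated, Listing 2 gives study duration per patient, and AEs and SAEs are listed individually. With at most 24 patients a reader could rebuild patient-time. Nor does leaving mean that events are lost. Protocol 8.3.2.2 makes sensor removal a reason for withdrawal, asks for end-of-study assessments at early exit if the subject permits, and follows patients discontinued for a device- or procedure-related AE until it resolves or stabilises. Protocol 8.3.2.4 requires contact attempts and contact with the treating doctor for those lost.

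Much of this stands, and it limits the size of the point. It does not remove it: an interval is itself descriptive and needs no test, the SAP already plans 95% intervals elsewhere, and listings do not replace a stated rate where incidence is to be compared with the literature.

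Three stronger readings are tempting and are not supported:

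- A reader might infer that the plan would treat zero SADEs as proof of safety. No passage says so. The plan only omits the figure that would show what zero leaves open.
- A reader might infer that drop-out will dilute the rates heavily. That needs a high or early drop-out, and no rate is given. Protocol section 5 expects some patients to be unwilling to take part for another two years, but this concerns joining the follow-up study, not leaving it.
- A reader might infer that the SAP defines the endpoint as a 24-month risk. It promises a count of patients with observed events. The understatement arises when the percentage is read as incidence over months 12–36, as the endpoint window and the literature comparison invite.

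**Conclusion.** The point holds as an improvement in reporting, not as a flaw that invalidates the safety analysis. The percentages for SADE and AE carry no interval and ignore follow-up time. The size of the first gap depends only on the cap of 24 and the 95% level: 0/24 leaves risks up to 14.2% open, and 1/24 leaves 0.1–21.1%. The direction of the second is sure whenever patients at continuing risk leave event-free. Its size rests on assumed drop-out, constant hazard and a 10% true risk; it is modest at 10–20% drop-out and about a fifth in relative terms at 40% spread evenly.

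**What to change.** In SAP 8.6.1 and 8.8.1 and the AE table shells:

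1. Keep the FAS as denominator. Completers alone would be worse, because patients withdrawn after sensor removal would drop out of the safety figures.
2. Add exact (Clopper-Pearson) two-sided 95% intervals to the proportions of patients with a SADE, SAE, ADE and AE. This shows precision; it does not correct for early leaving, so item 3 is also needed.
3. Beside each proportion, give the number of patients with a first event per patient-year with an exact Poisson interval, and print total patient-years. Count first events only: repeated AEs cluster within patients, and a Poisson interval on all events would be too narrow.
4. Count time from V09 to the first event or, without one, to the last documented contact or assessment. Do not reuse the duration in SAP 7.1. It runs to the later of the last visit and the discontinuation date, which can fall after the last contact and so inflate exposure.

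The cost is a few table columns, one additional derived variable, and safety figures that look less favourable. The items above require no new examinations.

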8.6.2 Performance

- Incidence, nature and seriousness of observed device malfunctions from V09 (month 12) throughout V13 (month 36). This parameter will be analysed using a frequency table.
- The variables
 - Standard deviation of 2 – 3 measurements using GAT system
 - Standard deviation of 2 – 3 measurements using ARGOS-SC system at visit V09 – V13 will be analysed descriptively per visit and overall.

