### **IOP measurement in the clinic**

IOP measurement will be conducted as a series of 2x GAT (in case of a difference of more than 2mmHg, a third GAT-measurement is required) followed by 3x ARGOS-SC system. When series of measurements are made, GAT must always be used first to avoid potential operator bias. For the ARGOS-SC measurements the patient has to stay in the same position as for the GAT-measurements (chin on chin rest, forehead installed).

Additionally (if available), a series of 2x DCT (in case of a difference of more than 2mmHg, a third DCT-measurement is required) followed by 3x ARGOS-SC will be performed after the series of GAT and ARGOS-SC measurements. For the ARGOS-SC measurements, the patient has to stay in the same position as for the DCT-measurements (chin on chin rest, forehead installed).

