 External eye photography is performed through a slit lamp camera or equivalent. The outer eye shall be photographed in order to document potential changes to the iris or pupil structure.

 Anterior segment OCT is performed to evaluate effects on change in chamber angle after non-penetrating glaucoma surgery and to assess corneal thickness.

 Slit-lamp biomicroscopy is performed through an undilated pupil to assess the following anatomic parameters of the anterior segment: lids, conjunctiva, cornea, anterior chamber, iris, pupil, lens and anterior vitreous body.

 Standard gonioscopy is used to confirm glaucoma classification and to evaluate the presence of iris tumors, foreign bodies, anterior synchiae and to predict the anterior chamber angle. The gonioscopic grading system according to Shaffer is used in this clinical investigation.

 Funduscopy is performed by means of indirect ophthalmoscopy on a slit lamp with the aid of a 90D or "Superfield" or comparable lenses. For this examination the pupil needs to be dilated by the use of mydriatic agents. This method is used to evaluate the following parameters: optic nerve lesions, other posterior pole lesions, vitreous opacities, optic nerve head, fundus lesions, retinal arteries and veins (AV), macular area, fundus periphery, normal and abnormal variations of the fundus.

 Posterior segment OCT is used to assess macular structures and the peripapillary nerve fiber layer thickness (RNFLT) and if possible Minimum rim width at Bruch membrane opening (BMO-MRW).

 The fundus should be photographed in order to document potential changes to the optic nerve (cup/disc ratio) and nerve fiber layer (red-free illumination).

 IOP measurements will be made in series of 2 GAT measurements (in case of a difference of more than 2 mmHg, a third GAT measurement is required) followed by 3 directly consecutive ARGOS-SC system measurements; *if DCT is available*: additionally followed by 2 Pascal DCT measurements (in case of a difference of more than 2 mmHg, a third Pascal DCT measurement is required) and 3 directly consecutive ARGOS-SC system measurements.

For the non-study eye, only GAT and DCT measurements will be performed as described above.

All measurements should be performed directly one after another.

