8.1.3 Level of significance

All analyses will be conducted descriptively, so that no statistical tests will be performed. All confidence intervals which will be calculated will be two-sided 95% confidence intervals.

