11.3 Statistical Analysis Package – Table of Contents

11.3.1 Tables

Table 1.1	Patient Disposition
Table 1.2	Baseline Characteristics
Table 2.1.1	IOP measures: GAT and ARGOS-SC
Table 2.1.2	IOP measures: DCT and ARGOS-SC
Table 2.2.1	User Acceptance Questionnaire for Investigator
Table 2.2.2	User Acceptance Questionnaire for Patient
Table 2.2.3	Standard deviation of IOP measures: GAT and ARGOS-SC
Table 2.3.1	Vision related Quality of Life Questionnaire
Table 2.3.2	Visual acuity (study eye)
Table 2.3.3	Visual acuity (fellow eye)
Table 2.3.4	Perimetry (study eye)
Table 2.3.5	Perimetry (fellow eye)
Table 2.3.6	Heidelberg Engineering ANTERION® (study eye)
Table 2.3.7	Heidelberg Engineering ANTERION® (fellow eye)
Table 2.3.8	Anterior segment (study eye)
Table 2.3.9	Anterior segment (fellow eye)
Table 2.3.10	Posterior segment (study eye)
Table 2.3.11	Posterior segment (fellow eye)
Table 3.1.1	Adverse Events
Table 3.1.2	Serious Adverse Events
Table 3.1.3	Device-related Adverse Events
Table 3.1.4	Device-related Serious Adverse Events
Table 3.2.1	Characteristics of Adverse Events
Table 3.2.2	Characteristics of Serious Adverse Events
Table 3.2.3	Characteristics of Device-related Adverse Events
Table 3.2.4	Characteristics of Device-related Serious Adverse Events
Table 3.3.1	Device Deficiencies
Table 4.1.1	Concomitant Medication of glaucoma
Table 4.1.2	Concomitant Medication of other indication

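### Repeatability is summarised as the mean of SDs from two or three readings, which understates sensor error by 11% and, at equal true error, makes ARGOS-SC look 11% to about 23% less repeatable than GAT

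*SAP*

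**What the plan says.** SAP 4.2.2 lists "Repeatability of ARGOS-SC measurement" as a secondary performance endpoint and attaches no estimator to it. The only analysis that fits is in SAP 8.6.2, which names two variables: "Standard deviation of 2 – 3 measurements using GAT system" and "Standard deviation of 2 – 3 measurements using ARGOS-SC system at visit V09 – V13 will be analysed descriptively per visit and overall". SAP 8.1.2.1 says what a descriptive analysis contains ("Continuous variables will be summarized using descriptive statistics, including" n, mean, SD, median, quartiles and range). SAP 11.3.1 puts both methods in one output, Table 2.2.3, titled "Standard deviation of IOP measures: GAT and ARGOS-SC".

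The number of readings comes from the measurement rules. Protocol 8.3.12.13 (clinic measurement) takes two GAT readings and adds that "in case of a difference of more than 2mmHg, a third GAT-measurement is required". Protocol Table 4, footnote 10, repeated under SAP Table 1, has the GAT readings "followed by 3 directly consecutive ARGOS-SC system measurements". So a scheduled ARGOS-SC series always has three readings, while a GAT series has two or three depending on what the first two show.

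Neither document specifies a pooled within-series SD, a repeatability coefficient or an adjustment for the number of readings.

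**The concern.** The SD of two or three readings is a skewed statistic whose expected value lies well below the true SD. Averaging many such SDs does not remove the shortfall, and its size depends on how many readings each SD uses.

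Two consequences follow if the plan is carried out as written. The sensor's measurement error, which is the endpoint, is reported as smaller than it is. And the GAT figure in the same table is too small by a larger factor, so the two cannot be read against each other, and any such reading is tilted against the sponsor's own device. The conditional third GAT reading adds to this: it enters only series whose first two readings lie far apart, and on average it pulls those SDs down.

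**Working it through.** **Inputs.** Three ARGOS-SC readings per series; two GAT readings, with a third if the first two differ by more than 2 mmHg (Protocol 8.3.12.13; Table 4, footnote 10). At most 24 patients and five visits, V09 to V13, hence up to 24 × 5 = 120 series per method. The plan states no repeatability figure, so there is none to reproduce, and it states no within-series SD, σ. Two values can be placed from the protocol, each by assumption: 2/3 = 0.67 mmHg, from the specified 3-sigma accuracy of 2 mmHg (section 4.7.1.4), and 5/1.96 = 2.55 mmHg, if the ±5 mmHg imprecision in section 3.3 is a 95% range. I show 0.5 to 3 mmHg.

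**Step 1: fixed number of readings.** For n independent normal readings, E[SD] = c4(n)·σ, with c4(n) = √(2/(n−1))·Γ(n/2)/Γ((n−1)/2).

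- c4(3) = 0.8862: the mean SD is 11.4% too low, at any σ.
- c4(2) = 0.7979: the mean SD is 20.2% too low.
- Ratio at equal σ: 0.8862/0.7979 = 1.111.

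**Step 2: conditional third GAT reading.** Let a and b be independent standard normal variables. The two-reading SD is σ|a| and the three-reading SD is σ√((a²+b²)/2). The latter is used when |a| > √2/σ, which is the same as a first difference above 2 mmHg. Numerical integration and simulation agree:

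| True σ (mmHg) | GAT series with third reading | GAT mean SD/σ | ARGOS-SC mean SD/σ | Ratio of mean SDs |
|---|---|---|---|---|
| 0.5 | 0.5% | 0.794 | 0.886 | 1.12 |
| 0.67 | 3.4% | 0.777 | 0.886 | 1.14 |
| 1 | 16% | 0.738 | 0.886 | 1.20 |
| 1.5 | 35% | 0.718 | 0.886 | 1.23 |
| 2 | 48% | 0.723 | 0.886 | 1.23 |
| 3 | 64% | 0.748 | 0.886 | 1.18 |

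The ratio peaks at 1.235 near σ = 1.56. At 2.55 it is 1.20. It returns to 1.11 at about 5.8 mmHg and tends to 1 beyond that, because the third reading is then almost always taken.

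**Step 3: the median.** The median SD is √(ln 2)·σ = 0.833σ for three readings and 0.674σ for two, a ratio of 1.23. With the third-reading rule the ratio runs from 1.22 to 1.33 over σ of 0.5 to 3. These values hold for continuous readings. If GAT is read to whole mmHg (an assumption), the median ratio becomes erratic: 0.59, 0.79, 1.18, 1.77 and 1.18 at σ of 0.5, 0.67, 1, 1.5 and 2. The ratio of means barely moves (1.11, 1.12, 1.17, 1.23, 1.24 and 1.21 at the six σ values in the table).

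**Step 4: visibility at this study size.** With σ = 1.5 for both methods and 24 eyes, the ratio of mean SDs has a 95% range of 0.88 to 1.79 at one visit, so the tilt is lost in noise. Over 120 series the range is about 1.05 to 1.44, and ARGOS-SC looks worse in over 99% of simulated studies although the errors are identical.

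**Step 5: the alternative.** Pool by degrees of freedom: s_w = √[Σ(nᵢ−1)SDᵢ² / Σ(nᵢ−1)]. For GAT this returned 0.999 to 1.001 of σ throughout, even with the conditional reading. The ratio over 120 series is then centred on 1.00 (95% range 0.87 to 1.15). The weighting matters: an equal-weight average of GAT variances gives only 0.87σ at σ = 1.5.

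**The case against.** The strongest reply is that no comparison is planned. The endpoint is the repeatability of ARGOS-SC alone, the SAP states that "All analyses will be conducted descriptively, so that no statistical tests will be performed", and no ratio or difference of the SDs appears anywhere. That is true. The tilt arises only when a reader sets the two entries of Table 2.2.3 side by side, though a table that holds both invites this. The 11% understatement of the sensor's own error needs no comparison.

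Second, for ARGOS-SC the pooled SD can be recovered from planned output. With three readings in every series it equals √(mean² + SD²·(n−1)/n), where mean and SD are those tabulated for the n series SDs. This is correct, but the plan does not do it, and the GAT figure cannot be recovered this way because its series differ in length.

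Third, the absolute effect is small: 0.114 × 0.67 = 0.08 mmHg, and 0.114 × 2 = 0.23 mmHg, against an agreement band of ±5 mmHg. This stands and limits the importance of the point.

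Fourth, equal true error is an assumption. If the sensor SD were 0.67 and the GAT SD 1, the true ratio of 0.67 would appear as 0.67 × 1.20 = 0.80: the ordering survives but the contrast is blunted. SAP 8.6.2 also allows two ARGOS-SC readings. A series with only two would understate σ by 20%, and the gap to GAT would shrink to between 0% and 11%. Protocol section 3.3 mentions digit bias and artefacts from repeated readings, so independent normal GAT errors are an idealisation. These points change the size of the distortion and do not make the mean SD a sound estimate of σ.

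**Conclusion.** The concern holds. As written, the plan reports a named secondary endpoint with a statistic that understates sensor error by 11% (normal, independent readings, three per series), beside a GAT figure that is low by 21% to 28% for σ of 0.5 to 3 mmHg. At equal true error, ARGOS-SC appears 11% to about 23% less repeatable than GAT for any σ up to about 5.8 mmHg, a range that includes both values that can be placed from the protocol. The effect is not discernible at a single visit but is consistent in the overall row. The study is descriptive and no success criterion rests on this endpoint, so this is a modest correction to one secondary result that should be made, and it leaves the study's conclusion alone.

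**What to change.** In SAP 8.6.2 and Table 2.2.3, make the main repeatability estimate for each method the within-series SD pooled by degrees of freedom, s_w as in step 5, per visit and overall. Give it a 95% confidence interval that allows for several visits per patient, for example a bootstrap over patients. If wanted, add the repeatability coefficient 2.77 × s_w. Keep the median, quartiles and range of the per-visit SDs as supporting description, with a footnote that they are not comparable between methods because the number of readings differs.

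The cost is one sentence in the SAP and one added row per method, from the same data. There are downsides:

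- The reported sensor error will be about 13% larger than the mean SD (1/0.886 = 1.13).
- s_w is sensitive to a single aberrant series, which the retained distribution would reveal.
- For GAT, s_w runs about 3% high if true SDs vary by about 30% between eyes (1.533 against 1.494 in simulation).
- With whole-mmHg GAT readings, s_w is 15% high at σ = 0.5, 4% at 1 and 2% at 1.5, because rounding is itself reading error.

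A simpler option for GAT is the root mean square SD of the first two readings only, which also returned 1.00σ but discards the third readings.
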